4.4 CO-ENROLMENT

Co-enrolment in LACI-3 and another research study will be assessed case-by-case following the Sponsor's co-enrolment policy (POL008 Co-enrolment Policy).

Co-enrolment assessment between LACI-3 and another CTIMP or interventional non-CTIMP (e.g., surgical, or implantable device) will consider the safety of study participants, the interventions involved, the participant burden, and the potential impact on the LACI-3 outcomes.

Before the co-enrolment begins, the permission for co-enrolment must be documented according to the Sponsor's policy.

Co-enrolment in LACI-3 with non-interventional research (e.g., sample only, questionnaire studies) will not require any formal documentation or authorisation from the sponsor. The chief investigators and sponsor should be consulted for guidance if required.

5. PARTICIPANT SELECTION AND ENROLMENT

5.1 IDENTIFYING PARTICIPANTS

The investigators from the patient's direct clinical care team at participating hospital sites will identify potential participants for LACI-3. These investigators may include delegated doctors, nurses, or other research staff undergoing specific trial training. Potentially participants may be identified when presenting for the first time with a new stroke or recurrent stroke during hospital attendance in the everyday clinical practice of investigators. Potential participants who presented to the stroke services of participating sites in the past may also be identified through screening of hospital record systems, outpatient's clinic appointments, local audit and other registries as are available at participating hospitals. Potential participants can be referred to the investigators for the eligibility assessment by the clinical staff or they can self-refer to the recruiting hospital team. Potential participants may also be identified from other relevant trials and observational studies where consent has been given for re-contact for future relevant research e.g., from the Rates, Risks and Routes to Reduce Vascular Dementia (R4VaD) Study.

The first LACI-3 approach will occur after the delegated investigator reviews the patient's medical records, diagnostic scan, and medication list and confirms eligibility.

This initial contact will occur in person, via phone, or post following local clinical practice by the delegated investigator. If the potential participant is interested in LACI-3, the Facts Sheet will be given with a short summary about the trial, followed by the Participant Information Sheet and verbal explanations, as required. The Facts Sheet can be included in the Invitation letter.

The potential participants can be approached for consent at least 24 hours after lacunar stroke symptom onset.

Randomisation cannot occur ≤24 hours after lacunar symptom onset, and in most cases ≤1 month, to avoid the period when guideline stroke secondary prevention advises prescription of dual antiplatelet drugs (aspirin, clopidogrel) for 28 days followed thereafter by single antiplatelet, usually clopidogrel in the UK. Once the dual antiplatelet phase is over, then participants meeting the criteria can be randomised.

There is no upper time limit after the lacunar stroke onset when the potential participants can be approached, recognising that lacunar stroke is a sign of small vessel disease which is a long-term condition, enabling the recruitment of participants who have had their stroke in the past, and helping to optimise the equity of access to the research. Although lacunar stroke is more common in men than women,61 and LACI-2 included more males than females as is typical of lacunar stroke, nonetheless we aim in LACI-3 to include a more balanced male to female sample.

5.2 CONSENTING PARTICIPANTS

The potential participants will be given as much time as they need to decide if they want to join the LACI-3 before signing the informed consent. Consent will only be taken from potential participants who, in the opinion of the delegated Investigator, have capacity to understand each aspect of the trial. Only investigators delegated by the local Principal Investigator can obtain the consent from potential participants.

After allowing time for consideration, clarifying any questions and emphasizing that patients may withdraw their consent to participate at any time without affecting their medical care, potential participants will be asked by the delegated investigator to sign the informed consent form. The written consent must be signed by the participant and a delegated investigator. The investigator is responsible for ensuring that the consent form is completed,

signed and dated by all parties prior to any protocol specific procedures being carried out. The consent must be obtained in person.

The participant will be asked as a part of the consent form to name on a contact form an additional contact who has given permission to the participant to provide the information during the follow-up visits, in the event the research teams cannot contact the participant directly, to monitor the participant progress, IMP symptoms, IMP resupply and for safety e.g., to follow-up on the reported events (outcomes, SAEs) and if new information is available or the study is stopped. The contact information for the nominated additional contact whose agreement participant have obtained will be stored only at the local hospital NHS research team.

The participant should receive a copy of the consent form and a copy of the contact form, a copy of the consent form and contact form should be filed in the patient's medical records whether paper or electronic (a PDF will be uploaded to the medical record on sites where medical records are only held electronically) and the original consent and contact form filed in the Investigator Site File (ISF).

The whole consent process should be documented in the medical notes for any future source data verification. This must include the information on when eligibility was confirmed and by whom, when consent was obtained, and the version of the PIS. Obtaining consent must be recorded in the trial database. The site research staff should upload a copy of the consent on the e-CRF.

5.3 SCREENING FOR ELIGIBILITY

Participant eligibility will be verified by a clinical trial physician after written informed consent has been obtained. Confirmation of eligibility will be recorded within the participants' medical records.

A delegated investigator (Principal investigator or other doctor) will review the brain scan and/or its report that diagnosed the lacunar stroke to confirm eligibility before approaching a potential participant for the informed consent.

The baseline information obtained after consent and required for randomisation will be recorded in the eCRF.

Screening logs will not be used as part of the data collection for this study.

5.4 INELIGIBLE AND NON-RECRUITED PARTICIPANTS

Participants who have been approached for the study and subsequently found to be ineligible but not consented will be informed of the reasons why and continue under the care of their physician. Patients found to be ineligible after signing the informed consent form will be recorded as 'consented but not randomised', will therefore not constitute part of the intention to treat population, will be excluded from the primary analysis and will not be followed for AEs.

5.5 RANDOMISATION

5.5.1 Randomisation Procedures

Randomisation cannot occur ≤24 hours after lacunar symptom onset, and in most cases ≤1 month, to avoid the period when guideline stroke secondary prevention advises prescription of dual antiplatelet drugs (aspirin, clopidogrel) for 28 days followed thereafter by single antiplatelet, usually clopidogrel in the UK. Once the dual antiplatelet phase is over, then participants meeting the criteria can be randomised.

Randomisation can take place on the same day as the consent visit at the clinic after obtaining the consent, if all required tests for eligibility criteria and the baseline information are available.

Investigators with delegated responsibility will collect and enter pre-randomisation baseline data on the web-based trial database.

The electronic randomisation system and trial database are hosted by the University of Nottingham as in LACI-2. Randomisation will be stratified by baseline MoCA score (\geq 26, 22-25, \leq 21) and minimised on the key prognostic variables of age, sex, NIHSS, mRS, time since index stroke, years of education, systolic BP (\leq />140), smoker (current/ex/never) similar to LACI-2.^{47,49} Years of education give an estimate of pre-morbid cognitive ability and predicts post-stroke cognitive impairment; BP and smoking predict recurrent stroke; delay since stroke reflects disease activity; age, sex and stroke severity are standard minimisation variables. This approach ensures concealment of allocation, minimises differences in key baseline prognostic variables, and improves statistical power. Randomisation will not be minimised by Centre because this may result in high rates of allocation prediction, but a prespecified post-hoc analysis by centre will be performed to investigate and adjust for heterogeneity of treatment effect by centre.

Randomisation will allocate a trial treatment, which will be prepared by the local participating Pharmacy.

Note that randomisation will be performed during normal office hours (09.00 - 17.00) and the trial allows for randomisation to occur any time beyond 24hrs after the stroke (if the eligibility criteria are met) with no upper time limit after the stroke. Therefore, in the event of computer failure (for example: server failure), the investigator will wait until the computer system is re-established to perform the randomisation. Normally, this would only be a few minutes to two hours. However, if this delay requires the patient to return on a separate occasion to collect the drugs, then a separate appointment will be made and the patient's travel expenses covered as per other trial visits or the drug supply may be sent by post for the next day delivery.

Patients will be randomised to one of the following at a 1:1 ratio as per Section 6.3:

- cilostazol versus no cilostazol
- ISMN versus no ISMN

resulting in a partial factorial comparison of cilostazol versus ISMN versus both drugs versus neither drug.

All participants will continue their usual prescribed guideline stroke prevention medication.

The randomisation algorithm will allocate a unique participant identifier which will be used to label the treatment pack containing the appropriate drug made up for the patient and dispensed by the local Pharmacy.

Participants with an indication for or contraindication to one of the trial drugs may still be randomised to the other trial drug. If a participant allocated to both trial drugs develops a contraindication to one of the trial drugs after randomisation into the trial, then they should discontinue that drug but continue to take the other trial drug. If a patient has to discontinue either or both drugs, they should continue to be followed up in the trial as planned (unless they withdraw from the trial). Patients should remain in follow up until the end of the trial follow up period, even if they discontinue trial drug, unless they withdraw from the trial. Drug discontinuation will be recorded.

The study will be performed open label. Placebo tablets are not available and masking by encapsulation is too complicated and expensive. However, blinding of outcomes is important to obtain unbiased information about tolerability, safety, and efficacy. As such, IMP adherence structured questionnaire and prescribed medications will be taken by site staff who are already unblinded to trial allocation, while ascertainment of the main cognitive and

clinical outcomes will be collected by central follow-up co-ordinators who are masked to treatment allocation. During the first month after the randomisation, when the IMP dose will be increased, the local hospital sites will ask about the IMP symptoms using structured questionnaire at one-two and three-four weeks. The central blinded trial co-ordinators will continue to ask participants about the IMP symptoms at 6, 12, and 18-months follow-up visits. A web-based system into which the participant can enter information directly may also be available for participants who are willing to use this method.

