IMP	Investigational Medicinal Product
ISF	Investigator Site File
ISMN	Isosorbide Mononitrate

ISRCTN	International Standard Randomised Controlled Trials Number
MHRA	Medicines and Healthcare products Regulatory Agency
MI	Myocardial Infarction
MMSE	Mini Mental State Examination
MRI	Magnetic resonance imaging
mRS	Modified Rankin Score
MOCA	Montreal Cognitive Assessment
p-CRF	Paper Case Report Form
PDE3	Phosphodiesterase 3
PGI2	Prostaglandin Inhibitor 2
PI	Principal Investigator
PROBE	Prospective randomised open blinded end-point
PIS	Participant Information Sheet
NIMP	Non-Investigational Medicinal Product
QA	Quality Assurance
QoL	Quality of Life
REC	Research Ethics Committee
SAE	Serious Adverse Event
SAR	Serious Adverse Reaction
SDV	Source Data Verification
SIS	Stroke Impact Scale
SPC	Summary of Product Characteristics
SOP	Standard Operating Procedure
SPS3	Secondary Prevention of Small Subcortical Strokes Trial
SUSAR	Suspected Unexpected Serious Adverse Reaction
SVD	Small vessel disease
TIA	Transient Ischaemic Attack
TICS	Telephone Interview for Cognitive Status
TMF	Trial Master File

TMG	Trial Management Group
tMOCA	Telephone Montreal Cognitive Assessment
UK	United Kingdom
ТМТ	Trail Making Test
TSC	Trial Steering Committee
WМН	White matter hyperintensity

TRIAL SUMMARY

Trial Title	LACunar Intervention (LACI) Trial-3: Assessment of efficacy and safety of cilostazol and isosorbide mononitrate to prevent adverse outcomes in patients with cerebral small vessel disease(lacunar) ischaemic stroke
Study Acronym	LACI-3
Clinical Phase	3
Trial Design	An investigator led, multicentre, prospective, randomised, controlled, open label, 2x2 factorial, blinded endpoint (PROBE) confirmatory trial. MHRA Scientific Advice has been incorporated into the trial design.

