- Contact at 6, 12, 18 months by phone to check drug adherence; BP, medication history and supplements, outcomes and safety; arrange IMP re-supply by post if applicable

Central:

- Contact at 6, 12 and 18 months by post to collect recurrent vascular events, cigarettes and alcohol use, mRS, drug symptoms, Stroke Impact Scale, EQ-5D-5L, EQ-VAS, and health economic parameters only at 18 months; outcomes and safety
- Contact at 6, 12 and 18 months by phone to collect cognitive outcomes: tMoCA, TICS, Concentration (from MMSE), Animal naming, Zung, outcomes and safety

Central follow-up at 6, and 12, 18 months will be by post and telephone, blinded to allocated treatment. A trained assessor who is part of the central trial team and based either at the University of Edinburgh or University of Nottingham and who is blinded to treatment and baseline clinical information, will first confirm with the local site team and/or GP that the participant is contactable. They will then contact the participant by post and phone to administer the questionnaires following a standardised script.

About three weeks before the anniversary of the participant's randomisation or the last follow-up visit, the site hospital team will contact a participant by phone to conduct the 6, 12, or 18 months follow-up visit and to arrange the IMP re-supply if relevant.

If the site hospital team confirms that the participant is still alive, the participant will be sent a postal central follow-up questionnaire (followed by a telephone reminder if no response is received).

The central follow-up paper questionnaire can be obtained by phone during the cognitive outcomes collection. If the follow up information cannot be obtained by either postal or telephone questionnaire the local research team will be asked to provide follow up information from the medical records or by contacting the GP.

If, after at least 5 attempts, a participant fails to complete the phone visit done by the hospital site or return the paper questionnaire or will not complete the cognitive testing done centrally, this will be recorded as lost to follow-up in the e-CRF and reviewed by the TSC and DMC.

LACI-3 Protocol

Version 2.0, 16 December 2024 IRAS ID: 1008629

Table 2 Study Assessments

Follow-up ^b													
V2	/2 V:	/3 V4			V5				V6 ^c				
1-2 week	week 3-4 w	ek	6 months			12 months				18 months			
Site	ite Sit	e S	Site Central +/- 3 weeks				Site Centra		ntral	al Site		Central	

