 - Status of the participant (available, lost to follow-up, declined, withdrawn, died)
 - tMOCA
 - TICS-M
 - Concentration (MMSE)
 - Animal naming
 - Zung (mood)
 - Outcomes and safety events
- **Month 18** telephone follow-up completed by the local site team:
 - Status of the participant (available, lost to follow-up, declined, withdrawn, died)
 - IMP compliance
 - Blood pressure
 - Medication list
 - Supplements
 - Outcome and safety events
 - Details of the investigator who completed the phone questionnaire
- Month 18 postal follow-up completed by the central blinded trial co-ordinators:
 - Status of the participant (available, lost to follow-up, declined, withdrawn, died)
 - Type of accommodation
 - Vascular events
 - mRS
 - Smoking cigarettes and alcohol use
 - IMP symptoms
 - Falls
 - Stroke Impact Scale
 - Quality of life (5D-5L/ EQ-VAS)
 - Health economic parameters
 - Employment status
 - Details of the person who completed the postal questionnaire
 - Month 18 telephone follow-up completed by the central blinded trial co-ordinators:
 - Status of the participant (available, lost to follow-up, declined, withdrawn, died)
 - tMOCA
 - TICS-M
 - Concentration (MMSE)
 - Animal naming
 - Zung (mood)
 - Outcomes and safety events

Follow-up data will be collected on paper and electronic CRFs. If a participant needs help completing the follow-up questionnaires due to, e.g., visual or hearing impairment, a carer or relative may assist with it, and it will be recorded on the e-CRF. **Outcomes and Serious Adverse Events CRF** will include any clinical trial outcome reported from the moment of randomisation until the last follow-up at 18 months and any SAE reported from randomisation until up two weeks after the last dose of IMP is administrated.

Outcome events will be reported on the e-CRF and reviewed by the members of the trial management group. The event adjudication process will include checking for duplicates as

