reported events may come from several sources (site research team, participant, follow-up questionnaire, GP or carer, friend, or relative). The relevant clinical, radiographic or pathological information about the reported event will be obtained from the site hospital research team, e.g., Outpatient clinic letter, Discharge summary, brain imaging and radiological report, and blood results. Patient identifiers will be redacted from these documents before sending for internal adjudication to confirm if the event is classified as the outcome. Any potential SAEs or SUSARS identified during the review process will be reported to the sponsor using online e-CRF.

The anonymised **brain scans** that diagnosed the qualifying lacunar stroke and any reported clinical outcomes will be stored in a separate imaging database described in section 8.3. The central research staff will check each brain scan to confirm that it relates to the correct participant, correct time of the event, includes the required imaging sequences, does not show other explanations for the symptoms and will make scan available for the readers.

All case report forms must be reviewed and approved by the ACCORD Monitor prior to use (see ACCORD SOP CR013 CRF Design and Implementation).

NOTE: All electronic case report forms are subject to Co-Sponsor approval (see section 8.3).

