10.9 PREGNANCY

Women of childbearing potential are defined as fertile following menarche (having not been free from menses for >1 year) and until becoming post-menopausal (no menses for 12 months without an alternative medical cause) unless permanently sterilised by hysterectomy, bilateral salpingectomy, and bilateral oophorectomy.

Women of childbearing potential must use a highly effective method of contraception from the time of screening until 34 days after discontinuing the trial drug (duration of the study drug clearance from the body plus 30 days duration of one ovulatory cycle).

The highly effective birth control methods include:

- combined (oestrogen and progestogen containing) hormonal contraception associated with inhibition of ovulation
- progestogen-only hormonal contraception associated with inhibition of ovulation
- intrauterine device
- intrauterine hormone-releasing system
- bilateral tubal occlusion
- vasectomised partner
 - for female participants, the vasectomised male partner should be their sole partner; the vasectomised partner must receive medical assessment of the surgical success
- sexual abstinence refraining from heterosexual intercourse during the entire period of risk associated with the trial treatments.
 - true sexual abstinence when this is in line with the preferred and usual lifestyle of the patient.
 - periodic abstinence (calendar, symptothermal, post-ovulation methods), withdrawal are not acceptable methods of contraception.

All methods of contraception must be used in combination with the use of a condom by the male sexual partner for intercourse, from the time of screening until 34 days after discontinuing study treatment.

Male participants must avoid unprotected sex with all sexual partners (by use of condoms) during the trial, and for a washout period of 3 months after the last dose of trial drug.

Women of childbearing potential must have a negative urine pregnancy test done as a part of the screening on the day of randomisation. If applicable, the central team will send the urine pregnancy test with the central follow-up paper questionnaire to do the pregnancy test after 4 days of discontinuing the trial drug.

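### Some of the protocol's own procedures can weaken the masked central assessment and adjudication on which this open-label trial relies

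*Protocol*

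**What the plan says.** The trial summary describes an "open label, 2x2 factorial, blinded endpoint (PROBE) confirmatory trial". Section 5.5.1 explains how the blinded endpoint is achieved without placebo: "IMP adherence structured questionnaire and prescribed medications will be taken by site staff who are already unblinded to trial allocation", while the main cognitive and "clinical outcomes will be collected by central follow-up co-ordinators who are masked to treatment allocation". Section 6.10 gives the same reason for leaving tablet adherence with the site. Section 6.9 requires the central assessor to be unaware of treatment and of baseline clinical information.

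Three other provisions bear on that safeguard.

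- **Symptom items.** Section 5.5.1: "The central blinded trial co-ordinators will continue to ask participants about the IMP symptoms at 6, 12, and 18-months follow-up visits". Sections 6.8, 6.9 and 7.2 put these items on the central postal form and the cognitive tests on a separate central phone contact. Section 6.9 then adds: "The central follow-up paper questionnaire can be obtained by phone during the cognitive outcomes collection". A note to the flow diagram in Section 3 says that symptom answers are stored in a masked part of the database.
- **Adjudication.** Section 7.2: "Outcome events will be reported on the e-CRF and reviewed by the members of the trial management group". The supporting papers include clinic letters and discharge summaries, and "Patient identifiers will be redacted from these documents before sending for internal adjudication". Section 6.9 specifies blinded adjudication for repeat brain scans only.
- **Pregnancy tests.** Section 10.9 says that, where applicable, "the central team will send the urine pregnancy test with the central follow-up paper questionnaire to do the pregnancy test", four days after trial drug is stopped. A footnote to the study assessments table in Section 6.9 also gives the dispatch to the central team.

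**The concern.** The protocol separates tasks so that whoever scores cognition does not learn about the tablets. The provisions above partly undo that separation.

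Participants know their allocation. If symptom questions precede or interrupt the cognitive tests in one call, the assessor may hear answers that suggest active drug before scoring the tMoCA, TICS and animal naming, which feed the 7-level primary endpoint.

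If adjudicators can read the drug list, the classification of recurrent stroke, TIA, MI and dementia is no longer clearly masked. This reaches beyond secondary outcomes, because Section 2.1.2 makes a clinical dementia diagnosis an input to the primary score.

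In an open-label trial, masked assessment is the main protection against assessor bias, so avoidable gaps deserve closing.

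**Working it through.** No figure in the protocol is in dispute and no arithmetic settles the point. The check is to set the provisions side by side.

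**1. Can one assessor hear symptom answers before scoring cognition?**
- Who asks about symptoms at 6, 12 and 18 months: the masked central team (5.5.1, 6.8, 6.9).
- Who administers the cognitive tests: the central team, by phone (6.9, 7.2).
- Default mode for symptoms: the postal form, separate from the cognitive call.
- Exception: the form may be taken by phone during the cognitive contact (6.9). Neither an order of questions nor a second assessor is required.
- Does the masked database section close the gap? It hides the stored entry from later users. It does not stop the person asking from hearing the answer.
- Are the answers informative? Section 1.2 says that both drugs cause headache, so they can be, but they do not identify an arm.

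Result: the written procedure permits exposure to clues before scoring. How often the phone route will be used is not stated.

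**2. Are event adjudicators shown to be masked?**
- Papers used: clinic letters, discharge summaries, imaging reports and blood results (7.2).
- Redaction named: patient identifiers. Treatment is not mentioned.
- Could such papers carry treatment? Section 8.2 has the GP told of the allocation, and Section 6.3 has a reduced tolerated dose written in the hospital notes. Trial-drug information therefore enters the routine clinical record.
- Reviewers: trial management group members (7.2). Section 11.1 lists a follow-up coordinator in that group and does not say that members are masked.
- Contrast: repeat scans have blinded adjudication stated explicitly (6.9).
- Link to the primary endpoint: dementia is a listed outcome event (Section 10 and the study assessments table), and a clinical dementia diagnosis is a component of the 7-level score (2.1.2).

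Result: masking is stated for scans but not for the clinical papers or their reviewers.

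**3. What can sending pregnancy tests show?**
- The test is timed to stopping trial drug. If kits go only to women who took drug, the sender learns drug versus neither, not which drug.
- Only women of childbearing potential are affected. LACI-2 had a median age of 64 and was 69.1% male (1.1), so the number is probably small.
- The protocol does not say whether the sender is also the cognitive assessor.

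Result: a minor route.

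Section 8.2 also lists adherence among the information collected by local investigators and central coordinators together. Read literally, this conflicts with 5.5.1 and 6.10. It may only be a joint list, so the conclusion does not depend on it.

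**The case against.** The case on the other side is substantial, and much of it stands.

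- **A reader might infer that the central team is unmasked, or that the symptom questions reveal the arm.** The protocol does not support that. Every arm is asked, the complaints are non-specific, all participants continue other stroke-prevention drugs, and Section 1.1 reports that initial symptoms such as headache settled in LACI-1. Postal self-completion is the default, web entry may be offered, and the central call follows a standard script. What remains is the one sentence allowing the phone route.
- **A reader might infer that treatment is left visible to adjudicators.** Section 7.2 does not say so. Removal of treatment is unstated, not excluded, and the trial is declared blinded-endpoint. The gap is that the protocol specifies redaction and names only identifiers.
- **A reader might infer that sending the kits proves that the assessor knows who is on drug.** The text says only that the central team sends them, where applicable.
- **A reader might want a number.** Any rate of biased scoring would be invented. The 7-level score is also derived from test subscores and a diagnosis and is not rated directly, so bias would have to enter through scripted item scoring or prompting.
- **Moving all symptom questions to the site looks like the obvious remedy.** It has a real cost: drug symptoms are a secondary endpoint (2.2.2), and Section 5.5.1 wants tolerability collected masked. That trade is unnecessary, because fixing the order or the assessor suffices.

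Participants may also volunteer their treatment during the cognitive call. No change in wording prevents that in a trial without placebo. It does not justify a procedure that invites it.

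**Conclusion.** The point holds as a cheap improvement to conduct. The protocol makes masked central assessment its safeguard, then permits symptom questions within the cognitive call, specifies adjudication redaction that omits treatment, and does not state that clinical adjudicators are masked. Pregnancy-test dispatch is a small additional route.

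The size of any bias cannot be estimated from the protocol. It gives neither the share of questionnaires that will be taken by phone nor any rate at which assessors correctly infer allocation. The conclusion rests on two assumptions: that some questionnaires will be taken by phone during cognitive testing, as Section 6.9 allows, and that some letters or summaries will mention a trial drug. It does not show that masking will fail. The sample size, alpha and analysis model are unaffected.

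**What to change.** - **Section 6.9:** keep the symptom items self-completed by post or web. If they must be taken by phone, ask them only after the cognitive battery is scored and locked, or have a different central staff member ask them.
- **Section 7.2:** redact trial-drug names and allocation as well as identifiers from adjudication papers, and state that those who adjudicate clinical events are masked.
- **Section 10.9 and the study assessments table:** have the unblinded site team send the pregnancy tests.
- **Section 8.2:** align the sentence on adherence with Sections 5.5.1 and 6.10.
- **Optional:** record the assessor's guess of allocation at 18 months, so that the success of masking can be reported.

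The cost is slightly more redaction work and a fixed order of questions in the central call. Symptom data would still be collected by masked staff.
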